5.0 Measures

5.1 Outcome Measures

- Clinician-Administered PTSD Scale (CAPS) Global Score, subscale scores (B, C, D, F), Diagnostic criteria Met score, Associated Features (#26, 27, 28, 29, 30)
- PTSD Diagnostic Scale (PDS) Score, Rating, Impairment

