6.0 Analyses

6.1 Study population

See protocol. All participants were diagnosed with chronic PTSD, met DSM IV criteria, and had Global CAPS scores of 50 or greater upon enrollment. They had either undergone psychotherapy, pharmacotherapy or both without a significant reduction in PTSD symptoms.

All clinical data will be presented in tabular listings. All analyses will be carried out with SPSS of Version 12.0 or higher.

Definitions of subject populations for analysis:

All Enrolled: All participants who signed an informed consent form and completed baseline measures.

Intention to treat: All participants who were randomized to a condition and underwent at least one experimental session. All available data will be used.

Per Protocol: All participants who completed Stage 1 and underwent assessment of PTSD symptoms two months after the second experimental session. Analyses may be conducted with and without a participant who corresponds to a major protocol deviation.

Partial crossover: All participants who completed Stage 2 as well as Stage 1.

Extended Assessment 1: All participants who underwent assessment two, six and twelve months after their third Stage 1 or Stage 2 experimental session.

Extended Assessment 2: All participants who underwent Stage 3

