6.4.1 Main analyses

Goal: To determine if there is a main effect of condition on PTSD symptoms and criteria for meeting PTSD, three weeks after the second experimental session and three weeks after the third experimental session 1.

Population: Intention to Treat and Per protocol

Data included in analyses: CAPS (Global Score, subscales, and Diagnostic criteria met)

Format of analyses: Repeated-measures ANOVA. If multiple scores from a single scale are assessed, Bonferroni corrections were applied.

Time: Baseline, 3 weeks after Exp. Session 2, 3 weeks after Exp. Session 3

Between-groups factors: Condition (125 mg MDMA, 25 mg MDMA)

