6.5.1 Main Analysis

Physiological Measures and SUD

Analysis #1

Goal: to test the presence of a main effect of condition (125 mg MDMA, 25 mg MDMA, 150 mg MDMA in Extended Assessment 2) on changes in vital signs and psychological distress,

Population: All enrolled, intention to treat, per protocol, partial crossover, Extended Assessment 2

Data included: Pre-drug average, maximum change (peak) and post-drug average SBP, DBP, HR, BT and SUD, number of participants with vital signs above clinical cut off and duration above clinical cut-off

Format of Analyses: One-way ANOVA per each experimental session, including sessions during Stage 1, Stage 2 and Stage 3

Between-Group Factor: Condition (125 mg MDMA, 25 mg MDMA, 150 mg MDMA in Extended Assessment 2)

Analysis #2

Goal: To test effects of condition, presence or absence of supplemental dose and time of session on physiological data and psychological distress during experimental sessions

Population: All enrolled, intention to treat, per protocol

Data included: Pre-drug average, maximum change (peak) and post-drug average SBP, DBP, HR, BT and SUD, number of participants with vital signs above clinical cut off.

Format of analysis: Repeated measures ANOVA

Time: Session (Experimental 1, Experimental 2, Experimental 3)

Between Groups Factors: Condition (125 mg MDMA, 25 mg MDMA) as between-group factor, and supplemental dose (given, not given) as second between-group factor.

Analysis #3

Goal: To test effects of condition, presence or absence of supplemental dose and time of session on physiological data and psychological distress during Stage 2 or Stage 3 sessions.

Population: Partial crossover, Extended Assessment 2

Data included: Pre-drug average, maximum change and post-drug average SBP, DBP, HR, BT and SUD, number of participants with vital signs above clinical cut off, and duration above clinical cut-off.

Format of analysis: Repeated measures ANOVA

Time: Crossover Session (Stage 2 Experimental Session 1, 2, and 3, Stage 3 Experimental sessions 1 and 2)

Between-Subjects factors: Supplement (present, absent)

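### PTSD diagnosis status, on its natural yes/no reading, is tested by repeated-measures ANOVA at 8 v 4 where one named exact test is needed

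*SAP*

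**What the plan says.** The goal in SAP 6.4.1 is "To determine if there is a main effect of condition on PTSD symptoms and criteria for meeting PTSD". The outcomes are listed together ("Data included in analyses: CAPS (Global Score, subscales, and Diagnostic criteria met") and one method covers them all: "Format of analyses: Repeated-measures ANOVA. If multiple scores from a single scale are assessed, Bonferroni corrections were applied". The visits are "Time: Baseline, 3 weeks after Exp. Session 2, 3 weeks after Exp. Session 3".

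SAP 5.1 names the variable only as part of "Clinician-Administered PTSD Scale (CAPS) Global Score, subscale scores (B, C, D, F), Diagnostic criteria Met score" and gives no coding. On baseline status, SAP 6.1 states: "All participants were diagnosed with chronic PTSD, met DSM IV criteria, and had Global CAPS scores of 50 or greater upon enrollment". Protocol 2.7.1 requires current DSM-IV PTSD for entry, and Protocol 2.7.3 says that the CAPS supplies that diagnosis.

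The same outcome is analysed by repeated-measures ANOVA in SAP 6.4.2 Analysis #2, by ANOVA or t-tests in Analysis #3, by ANOVA or linear regression in the demographic factors analysis, and by ANOVA in 6.4.3. SAP 6.5.1 applies one-way ANOVA per session (Analysis #1) to the "number of participants with vital signs above clinical cut off and duration above clinical cut-off". Its Analyses #2 and #3 use repeated-measures ANOVA for the same counts.

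The only categorical method for an outcome or process measure is in SAP 7.0, for the blinding guesses. Protocol 2.8.3 plans nonparametric methods for CAPS and PDS scores, partly because the sample is too small to check parametric assumptions. It names no test for diagnosis status.

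**The concern.** If the item is yes/no, ANOVA models a 0/1 variable as normal with equal variance in arms of eight and four. One of its three visits is constant by design. If no low-dose participant loses the diagnosis, that arm also has zero variance afterwards, and the error term comes from the full-dose arm alone. In the most extreme result there is no error term at all.

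At stake is whether the difference in loss of diagnosis is called significant. With so few possible tables, that can turn on the choice of test.

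**Working it through.** The documents give no rate, power or test result for this outcome, so there is no figure to reproduce.

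**Inputs.** Allocation is 8 full dose and 4 low dose (Protocol 2.8.1). Alpha is 0.05 (Protocol 2.8.3; sidedness not stated, two-sided used). Assumed: yes/no coding, and all 12 meeting criteria at baseline.

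**1. Effect of the constant baseline.** Let y = 1 if criteria are met. The between-subject part of the ANOVA uses each participant's mean, (1 + y1 + y2)/3. The baseline 1 is the same for everyone and cancels. A difference of 0.75 at both later visits averages to (0 + 0.75 + 0.75)/3 = 0.50. The error shrinks in proportion, so the main-effect F does not change.

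**2. One post-treatment visit.** With baseline constant, the ANOVA main effect equals the pooled t-test on 10 df:

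t = d / √[s²(1/8 + 1/4)], with s² = [8p₁(1−p₁) + 4p₂(1−p₂)]/10.

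- 5/8 v 0/4: s² = 1.875/10 = 0.1875; t = 0.625/√(0.1875 × 0.375) = 2.36; p = 0.040. Fisher: (56 + 8)/792 = 0.081.
- 6/8 v 0/4: s² = 1.5/10 = 0.15; t = 0.75/√(0.15 × 0.375) = 3.16; p = 0.010. Fisher: (28 + 28)/924 = 0.061.
- 8/8 v 0/4: s² = 0, so F is undefined. Fisher: 1/495 = 0.0020.

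There are 9 × 5 = 45 possible tables. The key ones in the hypothesised direction are below. Boschloo here is twice the one-sided p-value, maximised over the common rate.

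| No longer meeting criteria, full v low | ANOVA | Fisher | Boschloo |
|---|---|---|---|
| 5/8 v 0/4 | 0.040 | 0.081 | 0.064 |
| 6/8 v 0/4 | 0.010 | 0.061 | 0.02 |
| 7/8 v 1/4 | 0.030 | 0.067 | 0.0506 |
| 8/8 v 2/4 | 0.027 | 0.091 | 0.084 |
| 7/8 v 0/4 | 0.0007 | 0.0101 | 0.005 |
| 8/8 v 1/4 | 0.0012 | 0.0182 | 0.013 |
| 8/8 v 0/4 | undefined | 0.0020 | 0.001 |

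At 0.05 the first four rows and their mirror images (eight tables) are significant by ANOVA and not by Fisher. The reverse never occurs. Under Boschloo six of the eight still differ; 6/8 v 0/4 and its mirror do not. The 7/8 v 1/4 pair is borderline: if tables are ranked by the two-sided Fisher p-value instead, it falls to 0.036 and four of the eight differ.

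**3. Three visits.** If status is the same at both later visits, the same eight tables differ. For 6/8 v 0/4 the main effect stays at p = 0.010. The interaction is p = 0.001 uncorrected and 0.010 with Greenhouse-Geisser.

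**4. Type I error.** At a common rate of 0.5 the tables that ANOVA calls significant (counting 8/8 v 0/4 and its mirror) have probability 2 × (1 + 8 + 4 + 28 + 32 + 56 + 6)/4096 = 270/4096 = 0.066. This is the maximum; at rates of 0.1 and 0.9 it is 0.024. Fisher at 0.5 gives 2 × (1 + 8 + 4)/4096 = 0.006 and peaks at 0.007.

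**5. Bonferroni.** The family size is not stated. Assume six CAPS scores (Global, subscales B, C, D and F, diagnosis): alpha = 0.05/6 = 0.0083. Then 5/8 and 6/8 v 0/4 are non-significant by both ANOVA and Fisher. Four tables still differ: 7/8 v 0/4, 8/8 v 1/4 and their mirrors.

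**The case against.** The best defence is that ANOVA does little damage here. Its type I error exceeds 0.05 by at most 1.6 percentage points, and at the assumed Bonferroni level it stays below nominal (peak 0.007 against 0.0083). Much of the disagreement comes from Fisher, whose true error is below 1%. When status changes between visits (4/8 then 6/8 v 0/4), an exact permutation test on the three-visit mean gives 0.048 and agrees with ANOVA (0.020). The usual two-sided mid-p (Fisher's p minus half the observed table's probability) gives ANOVA's verdict in all eight discordant tables; for 5/8 v 0/4 it is (64 − 28)/792 = 0.045. Four of the eight run against the hypothesis.

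All of that stands, and it limits the size of the point. It does not supply a valid test. Mid-p rejects in the same tables as ANOVA, so it has the same error of up to 0.066 and does not guarantee 0.05. Boschloo, which does, still contradicts ANOVA in some tables. Neither ANOVA nor its p-value exists for the clearest possible result.

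A reader might infer that the constant baseline weakens the test of condition. It does not: only the averaged estimate shrinks. A reader might also take diagnosis status for the leading result. The documents do not say so: SAP 3.1 and Protocol 2.6 make the CAPS score primary, and diagnosis is one of several outcomes in the main analysis.

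**Conclusion.** The point holds in limited form. SAP 6.4.1 and the later sections that reuse its format give no suitable method for a binary outcome at 8 v 4. The choice of test changes the verdict at 0.05 in 8 of 45 one-visit tables against Fisher, and in six against Boschloo as defined above. It would be wrong to read this as serious false-positive inflation.

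Three assumptions carry the conclusion. Yes/no coding is inferred from the name and the goal; SAP 5.1 and 6.4.2 Analysis #4 also call the item a score. If it counts criteria, the two-by-two tests do not apply, but the coding must still be stated. Baseline uniformity rests on the entry rules. The T0 CAPS follows screening, and SAP 6.2 allows for entry deviations, so an exception is possible. The Bonferroni family of six is assumed.

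For the vital-sign counts the same mismatch of method applies, but its size has not been calculated.

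**What to change.** - In SAP 5.1, state how the diagnostic-criteria item is coded.
- If it is yes/no, remove it from the ANOVA in 6.4.1. Compare the proportions no longer meeting criteria three weeks after session 3, and separately three weeks after session 2. Use one exact test named in advance: Fisher, or Boschloo with its two-sided definition stated, but not mid-p. Report the risk difference with an exact 95% CI.
- Carry the change into 6.4.2 Analyses #2 and #3, the demographic factors analysis and 6.4.3. Where a two-group comparison does not fit, as in Stage 2 or with a continuous predictor, report diagnosis status descriptively. Protocol 2.8.3 already expects too few Stage 2 participants for formal analysis.
- In 6.5.1, compare the number of participants above each vital-sign cut-off by the same exact test, session by session.
- SAP 8.0 records that outcome data had already been presented. If the diagnosis results were known when the test was chosen, say so.

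This costs SAP wording only; no new data are needed. The downside is that an exact test is conservative at 8 v 4, so the p-value will usually be less favourable.

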2.8. Methods

2.8.1. Drugs and Dosage

Upon enrollment in the study, the participant will be randomly assigned to the Low Dose or the Fully Active Dose condition. Condition assignment will be performed with a table of random numbers generated by the Institute for Statistics, University of Bern. All study investigators will remain blind to condition assignment. If there is an adverse event or other emergency requiring knowledge of participant's condition assignment, the blind may be broken for an individual participant.

Participants in the Low Dose condition are assigned to receive an initial dose of 25 mg MDMA followed 2.5 hours later by a supplemental dose of 12.5 mg MDMA. Participants assigned to the Fully Active dose condition will receive an initial dose of 125 mg followed 2.5 hours later by a supplemental dose of 62.5 mg MDMA. Eight of 12 subjects, or 66.6%, will be assigned to the Fully Active dose condition, and 4 of 12, or 33.3%, will be assigned to the Low Dose condition.

The two doses of MDMA chosen for the Low Dose condition have been selected on the basis of their ability to produce minimal but detectable subjective effects (Grob et al. unpublished; Harris et al. 2002) and thus serve as an active placebo. The cumulative dose of 37.5 mg MDMA is not expected to produce a significant reduction in anxiety or a significant increase in access to emotionally upsetting material, though this dose may produce slight alterations in consciousness, such as increased relaxation or tension (Harris et al. 2002). The initial 125 mg dose of MDMA selected for the Fully Active Dose condition was chosen on the basis of case reports of MDMA-assisted psychotherapy conducted in the US prior to scheduling (Greer and Tolbert 1986), as well as on data obtained from [name] MAPS-sponsored MDMA/PTSD pilot study currently underway in the United States. This dose is expected to reduce fear in response to emotionally upsetting thoughts, feelings or memories and to increase access to emotionally intense material, and is thus expected to be therapeutically active. Doses equal to or exceeding 125 mg have been employed in previous uncontrolled and controlled studies of MDMA (Cami et al. 2000; Grob et al. 1996; Grob et al. Unpublished; Harris et al. 2002; Lester et al. 2000; Mas et al. 1999; Styk 2007; Tancer et al. 2001; Tancer et al. 2003; Vollenweider et al. 1998).

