2.8.2. Assessments and Measures

Psychiatric diagnoses will be made through the Structured Clinical Interview for Diagnoses (SCID), and PTSD symptoms will be measured by the Clinician Administered PTSD Scale (CAPS) during screening to determine whether an individual may participate in the study.

PTSD symptoms will be assessed six times in this study:

- T0: *Baseline assessment*
- T1: *Post MDMA 2 assessment*: 3 weeks after the second experimental session (MDMA 2)
- T2: *End of treatment assessment*: 3 weeks after the third experimental session (MDMA 3)
- T3: *1st follow-up assessment*: 2 months after the third experimental session (MDMA 3)

T4: *2nd follow-up assessment*: 6 months after the third experimental session (MDMA 3) for all participants assigned to the Fully Active Dose condition, and all participants assigned to the Low Dose condition who choose not to take part in the open-label study continuation.

T5: *3rd follow-up assessment*: 12 months after the third experimental session (MDMA 3) for all participants assigned to the Fully Active Dose condition, and all participants assigned to the Low Dose condition who choose not to take part in the open-label study continuation.

Participants who choose to take part in the open label study continuation “Stage 2” will be assessed identically to stage 1 three weeks after the second and third (end of treatment) experimental sessions and two, six and twelve months after the third experimental session in Stage 2. The T2 assessment will serve as baseline for stage 2.

Participants who choose to take part in the open label study continuation “Stage 3” will be assessed identically to stage 1 three weeks after the second (end of treatment) experimental session and two, six and twelve months after the experimental session in Stage 2. The T3 assessment will serve as baseline for stage 3.

All outcome measures will be administered by an independent assessor. The independent assessor will remain blind to subject condition and will not be present during psychotherapy sessions. The CAPS will serve as the primary outcome measure, and the PDS will serve as additional measure of PTSD symptoms. The CAPS and the PDS are specifically designed to assess PTSD. German versions of all measures will be used in this study.

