Statistical significance will be set at 0.05. Because the sample size is very small, the study has sufficient power only to detect large effects. Therefore, there will be no adjustment for multiple testing; p-values and confidence intervals will be reported instead. We will assess participant CAPS and PDS scores at baseline and two months after each participant has undergone a final session, defined as the last experimental or open-label MDMA-assisted psychotherapy session, using the same nonparametric tests employed in comparisons of active placebo and experimental dose MDMA described above.

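### SAP 6.4.1 applies Bonferroni, with no divisor, to a set of scores that includes the CAPS Global Score, while protocol 2.8.3 tests the primary outcome at 0.05 without adjustment

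*SAP*

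**What the plan says.** **Protocol.** Section 2.8.2 fixes the primary outcome: "The CAPS will serve as the primary outcome measure". Section 2.8.3 fixes the level: "Statistical significance will be set at 0.05". It then explains that so small a sample can detect only large effects, and concludes: "Therefore, there will be no adjustment for multiple testing; p-values and confidence intervals will be reported instead".

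**SAP.** Section 6.4.1 gives the data for the main efficacy analysis as "CAPS (Global Score, subscales, and Diagnostic criteria met"), analysed by repeated-measures ANOVA. The multiplicity rule in that section is: "If multiple scores from a single scale are assessed, Bonferroni corrections were applied". Section 5.1 itemises the CAPS scores as "Global Score, subscale scores (B, C, D, F), Diagnostic criteria Met score", followed by the associated features, which 6.4.1 does not include.

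The SAP does not mention the protocol's no-adjustment rule or explain leaving it. It does not state the number of scores to divide by, order the tests, or say whether the Global Score is tested before or alongside the others. Section 6.4.2 repeats the Bonferroni rule for Analyses #2 and #3. Analysis #1 there uses only the PDS Severity Score and carries no correction.

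**The concern.** A trial needs one decision rule for its primary outcome, and these documents give two. The protocol tests CAPS at 0.05. The SAP, read literally, tests the CAPS Global Score at 0.05 divided by an unstated number, because its own data list meets the condition that triggers the correction. A p-value between the two thresholds would be significant under one document and not under the other. With no divisor written down, whoever runs the analysis decides where the line falls.

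The literal reading also disturbs the order of the endpoints. The primary score would face a stricter threshold than the PDS Severity Score, which SAP 3.2 places among the secondary objectives. The subscales come from the same scale as the Global Score, so Bonferroni is likely to be conservative for this set. With 12 patients, the protocol's stated reason for not adjusting was lack of power.

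**Working it through.** The documents contain no power calculation, so there is no planned figure to reproduce.

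**Inputs from the documents**
- Level 0.05, unadjusted (protocol 2.8.3).
- Allocation: "Eight of 12 subjects, or 66.6%, will be assigned to the Fully Active dose condition" (protocol 2.8.1), so 8 v 4. Protocol 2.7 replaces drop-outs, so 12 analysed patients are assumed.
- Number of scores: SAP 5.1 gives Global (1) + subscales B, C, D, F (4) + diagnosis (1) = 6. SAP 6.4 refers to selected subscales. With only B, C and D the count is 5.

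**Assumptions not in the documents**
- Two-sided testing.
- Effect size, shown from 1.0 to 2.5 SD.
- The Global Score shares the correction.
- The protocol's CAPS score is the SAP's Global Score.

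**Thresholds.** 0.05/6 = 0.0083; 0.05/5 = 0.01.

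**Power, two-sample t-test.** Degrees of freedom = 8 + 4 − 2 = 10. Noncentrality = d / √(1/8 + 1/4) = d / 0.612. Power is the probability that a noncentral t variable exceeds the critical value, which is 2.228 at 0.05, 3.169 at 0.01 and 3.277 at 0.0083. At d = 1.5 the noncentrality is 1.5 / 0.612 = 2.45.

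| Difference (SD) | 0.05 | 0.05/5 | 0.05/6 |
|---|---|---|---|
| 1.0 | 31.5% | 11.6% | 10.2% |
| 1.5 | 59.9% | 30.1% | 27.4% |
| 2.0 | 83.7% | 56.0% | 52.6% |
| 2.5 | 95.6% | 79.2% | 76.5% |
| Detectable with 80% power | 1.90 SD | 2.52 SD | 2.59 SD |

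Power kept with six scores, relative to 0.05: 27.4/59.9 = 0.46 at 1.5 SD, 52.6/83.7 = 0.63 at 2.0 SD and 76.5/95.6 = 0.80 at 2.5 SD. With five scores at 1.5 SD it is 30.1/59.9 = 0.50.

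**Tests closer to those planned.** These were simulated at 1.5 SD and compare 0.05 with 0.05/6. The ANOVA rows use three time points, equal correlation between visits, and the effect present at both post-baseline visits.

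| Test | Correlation | 0.05 | 0.05/6 |
|---|---|---|---|
| Exact Mann-Whitney | n/a | 56% | 24% |
| ANOVA, main effect of condition (SAP goal) | 0.3 | 52% | 22% |
| | 0.5 | 43% | 17% |
| | 0.7 | 38% | 13% |
| ANOVA, condition-by-time interaction (protocol's main interest) | 0.3 | 50% | 22% |
| | 0.5 | 65% | 34% |
| | 0.7 | 87% | 61% |

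The correction costs power in every row. The interaction keeps 34/65 = 0.52 of its power at correlation 0.5 and 61/87 = 0.70 at 0.7.

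**The case against.** The strongest reply has four parts.

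- **The SAP states no threshold.** Its sentence is conditional, and neither a divisor nor a family is written down. This stands: 0.0083 is an inference from SAP 5.1, and the textual defect is an undefined family that conflicts with the protocol.
- **The loss depends on the scenario.** A reader might infer that the correction more than halves power in general. The documents do not support that. They give no effect size, sidedness or divisor, and the statement fails with five scores at 1.5 SD, with six scores at 2.0 SD or more, and for the interaction at correlation 0.5 or more.
- **The correction has a purpose.** SAP 3.1 speaks of CAPS scores without singling out the Global Score. For six co-equal scores, Bonferroni does control the family-wise error. This stands for the set as the SAP lists it, but it does not explain why the protocol's primary outcome became one of six.
- **The trial is exploratory.** Protocol 2.6 hypothesises only trends, a stricter threshold does not inflate type I error, and a reader with the raw p-value can undo the correction. This limits the damage. However, the protocol still sets a significance level, and the SAP does not promise the raw p-value.

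A reader might also infer from the past tense of the SAP sentence, and from the conference presentations in SAP 8.0, that the threshold was chosen after results were seen. The documents do not show this. The SAP uses the past tense widely, the same rule is in the future tense in 6.4.2, and a stricter threshold does not favour a positive result.

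**Conclusion.** The conflict holds on the text alone and needs no assumption: protocol 2.8.3 forbids adjustment, and SAP 6.4.1 applies it to a set that contains the primary score, with neither an exemption nor a divisor.

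Its size is conditional. If the Global Score shares the correction with four or five other scores, and for a two-sided t-test with 8 v 4 patients, power falls from 32% to 10-12% at 1.0 SD and from 96% to about 77-79% at 2.5 SD, with intermediate effects as tabulated. The difference detectable with 80% power grows by about 0.6 to 0.7 SD (2.52 − 1.90 = 0.62; 2.59 − 1.90 = 0.69). The proportional loss shrinks as the effect grows, and for the interaction as within-patient correlation rises. No claim about when or why the SAP's rule was chosen is needed, and none is supported.

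**What to change.** In SAP 6.4.1, state that the CAPS Global Score is the single primary test at two-sided 0.05, following protocol 2.8.3. Make the subscales and the diagnosis secondary. Either report them unadjusted with confidence intervals, as the protocol provides, or apply Bonferroni among themselves with the divisor written down (five if B, C, D, F and diagnosis are all kept). In either case, report the unadjusted p-value and confidence interval for the Global Score.

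The change needs no new data, but it has two costs. The secondary CAPS scores carry less confirmatory weight. Also, SAP 8.0 records that outcome data were presented in 2010 and 2011, so relaxing the SAP's threshold now is not a blind edit. It must be disclosed and justified as a return to the rule that the protocol had already set.
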